Safety and Efficacy of Donepezil in Mild to Moderate Alzheimer's Disease: A Multi-center

Single-arm Study in China

NCT02787746

September 18, 2016

Statistical Analysis Plan (SAP)

Safety analysis is conducted on the safety set (SS, patients who receive at least one dose of donepezil 10mg/day and have at least one safety evaluation). Efficacy analysis is conducted on the per protocol analysis set (PPS, patients who complete the study with no major protocol violations) with last observation carried forward (LOCF) as well as the full analysis set (FAS, all enrolled patients are included) LOCF. In addition, in order to test the robustness and accuracy of our results, efficacy analysis is further conducted on the PPS and FAS wherein missing data is not filled in and not included and thus only actual data of every patient who take the efficacy test are included (FAS [actual number] and PPS [actual number], respectively).

For the safety analysis, overall incidence of AEs and SAEs, incidence of AEs and SAEs by organ systems, severity, and AEs' relationship to donepezil are calculated and/or assessed by calculating the number of patients having AEs and SAEs, the prevalence of AEs and SAEs and their 95% confidence intervals (95% CI). Laboratory abnormalities such as changes in alanine aminotransferase (ALT) and aspartate aminotransferase (AST), and changes in EKG and ECG such as HR, QT, QTc are summarized and described using means, standard deviation (SD), median, maximal, minimal, 25th and 75th percentile values, and further analyzed with paired *t*-test. Correlations of AEs and various risk factors are first assessed with univariate logistic regression analysis, and variables included patients' medical history (history of neurological, cardiovascular, mental, liver and gastrointestinal diseases), age (grouped into ≤ 75 and > 75 years), gender, body weight (≤ 55 kg and > 55 kg), APOE genotype ($\epsilon 2/\epsilon 2$, $\epsilon 3/\epsilon 3$, $\epsilon 4/\epsilon 4$, $\epsilon 2/\epsilon 3$, $\epsilon 2/\epsilon 4$, and $\epsilon 3/\epsilon 4$), the presence or absence of APOE $\epsilon 4/\epsilon 4$, concomitant medications (cardiovascular and cerebrovascular, gastrointestinal, liver, neurological, mental and hypoglycemic medications), and duration of donepezil 5mg/day treatment prior to the study (days). Forward stepwise multivariate logistic regression analysis is subsequently performed to

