further assess correlations between various risk factors and incidence of AEs using variables chosen from those used in the univariate analysis (SLSTAY=0.3, a significance value of 0.3 is required for a variable to stay in the multivariate model).

MMSE and ADCS-ADL are assessed at each visit. Their changes at each visit from baseline are calculated. Factors affecting MMSE and ADCS-ADL changes are assessed with a mixed model-repeated measures using an autoregressive covariance structure. Variables are the same as those used in the univariate analysis of correlations between AEs and various risk factors

All analyses are performed with SAS 9.4 (SAS Institute Inc.; Cary, NC, USA), data is analyzed with a two-tailed hypothesis, and a *p* value < 0.05 is considered to indicate statistical significance.

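### Age and body weight enter the SAP's risk-factor models only as two-level variables, which is inefficient if their effects are gradual; continuous terms would cost almost nothing.

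*SAP*

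**What the plan says.** The SAP has no numbered sections. Its safety paragraph starts the risk-factor work with one-at-a-time models: "Correlations of AEs and various risk factors are first assessed with univariate logistic regression analysis". In the list of variables, age follows the medical-history items, at "gastrointestinal diseases), age (grouped into". Age and weight are given as "age (grouped into ≤ 75 and > 75 years" and "body weight (≤ 55 kg and > 55 kg". These are the variables for the models, not categories for a display table.

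The forward stepwise logistic model is then built "using variables chosen from those used in the univariate analysis". For the mixed model of MMSE and ADCS-ADL change, the SAP states: "Variables are the same as those used in the univariate analysis of correlations between AEs and various risk factors".

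The same list includes "duration of donepezil 5mg/day treatment prior to the study (days", with a unit but no cut. Neither document explains why 75 years or 55 kg was chosen. Neither plans a continuous, spline or sensitivity version of age or weight.

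**The concern.** Both variables are continuous measurements that the trial already holds. The protocol's inclusion criteria admit patients aged 50 to 85, so the lower age group covers 25 of the 35 eligible years. A patient of 50 and one of 75 are modelled as identical, while patients of 75 and 76 differ by the whole age effect. Weight has no eligibility limit, so the upper weight group is open-ended.

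If risk changes gradually with age or weight, the two-level version has less power to detect it, both for adverse events and for MMSE or ADCS-ADL change. A multivariable model that retains either variable also adjusts for it only coarsely. Because the cut variables feed all three kinds of model, no planned analysis would recover the loss.

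**Working it through.** **Plan's own figure.** The documents state no power or precision figure for these models. The only sample-size figure is 461 evaluable patients (protocol section 1.1), set so that a 95% interval around 76% incidence is 8 percentage points wide. It reproduces with the exact Clopper-Pearson interval (n × 0.76 left unrounded). It is used below only as an illustrative n.

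**Inputs from the documents.** Cuts at 75 years and 55 kg, two-sided 5% tests (SAP); ages 50–85 (protocol, eligibility criteria); 76% incidence (protocol section 1.1).

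**Assumed, because the documents are silent.** The shape, mean and SD of age and weight, and an effect linear on the model scale.

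**Step 1: information kept by one cut.** For a linear effect this is the squared correlation between the covariate and its two-level version. For a normal covariate with a fraction q on one side of the cut:

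kept = φ(z_q)² / [q(1 − q)]

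| Split | Calculation | Kept | Lost |
|---|---|---|---|
| 50/50 | 0.3989² / 0.25 | 0.637 | 36% |
| 40/60 | 0.3863² / 0.24 | 0.622 | 38% |
| 30/70 | 0.3477² / 0.21 | 0.576 | 42% |
| 25/75 | 0.3178² / 0.1875 | 0.539 | 46% |
| 20/80 | 0.2800² / 0.16 | 0.490 | 51% |

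The median split is the best case for a normal covariate.

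**Step 2: other shapes.** For a uniform covariate, kept = 3q(1 − q).

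- Cut at the median: 3 × 0.25 = 0.75, a loss of 25%.
- Age uniform on 50–85, cut at 75: 3 × (25/35) × (10/35) = 0.612, a loss of 39%.
- True step exactly at the cut: the two-level variable is the correct model and loses nothing.

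**Step 3: the actual cut-points over assumed distributions.**

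- Age, normal truncated to 50–85, underlying mean 66–78 and SD 7–12: loss 33% to 66% (about 42% at mean 72, SD 8). The lowest values need an age distribution centred near 75.
- Weight, normal, mean 55–65 kg and SD 8–12: loss 36% to 65% (about 42% at mean 60, SD 10).

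**Step 4: simulation check.** Univariate logistic model, n = 461, 76% risk at the covariate mean, effect linear on the logit scale, 1,500 replicates (Monte Carlo standard error at most √(0.25/1500) = 1.3 points). Age has underlying mean 72, SD 8; weight has mean 60, SD 10.

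| Covariate | Odds ratio per SD | Power, continuous | Power, cut |
|---|---|---|---|
| Age | 1.20 | 40% | 24% |
| Age | 1.35 | 79% | 54% |
| Weight | 1.20 | 39% | 26% |
| Weight | 1.35 | 78% | 59% |

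The squared ratio of mean z statistics, cut to continuous, was 0.54–0.55 for age and 0.61–0.63 for weight. These lie either side of the 0.58 that step 3 implies for both.

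**The case against.** The cuts are pre-specified, so the bias of data-driven cut-points does not arise. Grouped age and weight are common in an exploratory screen and easy to read. Age and weight effects are not endpoints: the only risk-factor endpoint in protocol section 1.4 is APOE genotype against adverse events. All of that stands, and it limits the importance of the point. It is also true that if risk really steps at the cut, a linear term is the less efficient choice. The SAP claims no such threshold.

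A reader might infer more than the documents support:

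- **That a third or more of the information is certainly lost.** That figure depends on a roughly normal covariate and a linear effect, and the documents establish neither. The loss could be 25% or nothing.
- **That the plan discards about 167 to 212 of 461 patients.** This multiplies 461 by 0.363 and 0.461. But 461 is the target for the width of the primary interval, whereas the adverse-event models belong to the safety-set analysis, whose size is not stated. The loss also applies only to tests of age and weight, not to the trial's information as a whole.
- **That APOE and comorbidity estimates are left confounded.** The univariate models adjust for nothing, so the coding of age cannot matter there. The stepwise model may retain neither variable. Where one is retained, coarse adjustment is possible, but its size and direction cannot be worked out from the documents.
- **That the SAP is inconsistent because prior 5 mg duration stays continuous.** The SAP gives days as the unit but does not say how duration enters the model. Likewise, identical coding in the mixed model is the natural reading but is not explicit.

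**Conclusion.** The point holds as a minor improvement to secondary analyses. The SAP offers age and weight to the univariate models only in two-level form and carries those variables into the stepwise and mixed models, without a reason or a continuous alternative. With roughly linear effects and roughly normal covariates, the loss on the affected covariate is about 36% at a median split and 46% at a 25/75 split. Over the assumed distributions it could reach about 65%. These figures are conditional on assumptions that the documents cannot confirm.

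The loss concerns the tests of age and weight, and any adjustment for them in multivariable models that retain them. It does not touch the primary adverse-event incidence or its confidence interval, nor the paired before-and-after analyses of MMSE and ADL in protocol section 1.7.

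**What to change.** Amend the SAP's list of model variables:

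1. Enter age (per 5 years) and body weight (per 5 kg) as continuous linear terms in the univariate logistic, stepwise logistic and mixed models.
2. Check linearity outside the stepwise selection with a three-knot restricted cubic spline for each variable, so that the selection procedure itself is unchanged.
3. Keep the 75-year and 55-kg groups for descriptive adverse-event tables.

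The linear terms use the same one degree of freedom each as the two-level terms. The spline check adds one per variable. No new data, visits or patients are needed. The price is a little extra analysis and effect estimates that are slightly less easy to read.

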**Safety and Efficacy of Donepezil in Mild to
Moderate Alzheimer's Disease: A Multi-center
Single-arm Study in China**

Protocol & SAP Synopsis

2016.10.09

NCT02787746

PROTOCOL TITLE	Safety and Efficacy of Donepezil in Mild to Moderate Alzheimer's Disease: A Multi-center Single-arm Study in China
STUDY SPONSOR	Beijing Friendship Hospital & Eisai (China) Pharmaceutical Co., Ltd.
STUDY PHASE	4
INDICATION	For the treatment of mild to moderate Alzheimer's disease.
PRIMARY ENDPOINT	Monitoring and recording the count and incidence of adverse events (AEs).
SECONDARY ENDPOINTS	
 • Monitor and record the number of patients withdrew from trial for adverse events. • Change from baseline to 20 weeks in MMSE scores. • Change from baseline to 20 weeks in ADL scores. • Correlation analysis between Apo-E genotyping and adverse events of donepezil.
STUDY DESIGN	This is a Phase 4 multi-center, single-arm, open labeling study.
SAMPLE SIZE	The main indicator of this study was the incidence of adverse events in the treatment of Alzheimer's disease with 10 mg donepezil hydrochloride tablets. According to the safety data in the comprehensive literature, the incidence of adverse events is basically between 69.4%-81%, and the expected total incidence of adverse events is about 76%, estimated with a 95% confidence interval. With reference to the research data, the width of the confidence interval for the incidence of adverse events is 8%, and the significance level is set as 0.05. The sample size is estimated to be 461 cases by using PASS11.0 software. Considering the 20% drop out rate, 554 cases are finally planned to enter the group.

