ELIGIBILITY CRITERIA	
Inclusion Criteria:
 
 1. Patients between 50 and 85 years of age. 2. Patients newly diagnosed as probable AD based on Diagnostic and Statistical Manual of Mental Disorders, 4th Edition, Text Revision (DSM-IV-TR) criteria and National Institute of Neurologic and Communicative Disorders and Stroke—AD and Related Disorders Association (NINCDS-ADRDA) criteria; Mild to moderate AD with Mini-Mental State Examination (MMSE) 10-24, modified Hachinski ischaemic scale (MHIS)≤4, Activity of daily life scale (ADL)≥23, and Hamilton Depression Scale (HAMD) <7. 3. MRI image supports the diagnosis of AD (medial temporal lobe atrophy, Fazekas scale of white matter lesions≤2 within 6 months prior to the screening). 4. 5mg daily of Donepezil for at least four weeks before the screening. 5. Patient with exclusive caregiver. 6. Patient should be ambulatory or ambulatory aided by a walker or cane. 7. With good eyesight and hearing, can cooperate with the examination and treatment. 
Exclusion Criteria:
 
 1. Patients with vascular dementia, other types of dementia or with other psychiatric or neurological disorders (e.g. delirium, depression, Parkinson's disease, etc.). 2. Patients with type I diabetes, obstructive lung disease or asthma, vitamin B₁₂ or folic acid deficiency, thyroid dysfunction, severe liver or kidney dysfunction, severe cardiac insufficiency (congestive heart failure, myocardial infarction, sick sinus syndrome, II-III degree atrioventricular block or heart rate<50 beats/minute [bpm]). 3. Epilepsy or head trauma resulting in unconsciousness that occurred in the two years prior to the screening. 4. Patients with hematologic diseases (such as anemia, granulocytes, leukemia, etc.), tumor, neoplasms within 2 years prior to the screening. 5. Patients with a history of alcohol dependence and drug abuse. 6. Patients with known hypersensitivity to medicines or
----------------------	---

	
foods;
 
 7. Patients taking anticholinergic agents or antihistaminic agents; 8. Patients who had been hospitalized continuously for more than 3 months before the screening.

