1.4 Efficacy Endpoints

- Primary Efficacy Endpoints

Monitoring and recording the count and incidence of adverse events (AEs).

- Secondary Efficacy Endpoints

1. Monitor and record the number of patients withdrew from trial for adverse events.
2. Change from baseline to 20 weeks in MMSE scores.
3. Change from baseline to 20 weeks in ADL scores.
4. Correlation analysis between Apo-E genotyping and adverse events of donepezil.

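### The APOE secondary endpoint is worded around donepezil's adverse events, but its only planned model counts AEs of any cause; the same model should also be run on AEs assessed as drug-related

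*SAP*

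**What the plan says.** The protocol synopsis and section 1.4 list as a secondary endpoint "Correlation analysis between Apo-E genotyping and adverse events of donepezil". Section 1.7, which sets out the analysis of the secondary indicators, covers withdrawals for AEs, MMSE and ADL, and gives no method for this endpoint.

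The method is in the SAP. "Correlations of AEs and various risk factors are first assessed with univariate logistic regression analysis", with APOE entered as six genotypes and as presence or absence of ε4/ε4. A forward stepwise multivariate model follows, to "further assess correlations between various risk factors and incidence of AEs using variables chosen from those used in the univariate analysis". Neither step limits the outcome by cause.

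The same SAP paragraph treats causality separately: "AEs' relationship to donepezil are calculated and/or assessed by calculating the number of patients having AEs and SAEs", with rates and 95% confidence intervals. This classification is tabulated and is not carried into the regression.

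On design, the synopsis states "This is a Phase 4 multi-center, single-arm, open labeling study". Inclusion criterion 4 requires "5mg daily of Donepezil for at least four weeks before the screening". The safety set is "patients who receive at least one dose of donepezil 10mg/day and have at least one safety evaluation".

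**The concern.** The endpoint names the drug as the source of the events, whereas the model counts every event. Patients are 50 to 85 years old and have dementia, so some AEs over 20 weeks will come from age, the disease or other illness. Everyone in the safety set is on 10 mg, and everyone took 5 mg before screening. The trial therefore has no untreated group and no drug-free period to show the background rate. The relationship assessment is the only item in the plan that tries to separate the two kinds of event, and the APOE model does not use it.

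Two consequences should be kept apart. The outcome definition causes dilution: background events unrelated to genotype pull a real association with drug-related AEs towards no effect. The lack of a comparator causes ambiguity: an APOE association with background events alone would look the same in this model. At stake is what the trial can say about one named secondary endpoint.

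**Working it through.** **The plan's own figure.** The protocol's 461 is the smallest n for which an exact (Clopper-Pearson) 95% interval around 76% has full width 8%. The planned 554 is 461 × 1.2, rounded up. These figures size the precision of the any-AE incidence. Neither document gives a power or sample size for the APOE analysis.

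**Inputs.** From the documents: 461 patients, any-AE incidence 76%, two-sided alpha 0.05. Assumed, because the documents are silent: related-AE incidence r of 30-50%, background AEs independent of related AEs and of genotype, a binary genotype group holding a share f of 30-50%, and a true odds ratio (OR) of 2 on drug-caused AEs.

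**Formulas.**
- Any-AE risk = 1 − (1 − r)(1 − u), with background risk u set so that the overall risk is 76%: u = 1 − 0.24/(1 − r).
- Wald power = Φ(z − 1.96) + Φ(−z − 1.96), with z = ln(OR)/SE and SE² = 1/(n₀p₀(1−p₀)) + 1/(n₁p₁(1−p₁)).
- Judged relatedness with sensitivity and specificity both s: observed risk = s·r + (1 − s)(1 − r).

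**Worked case, r = 40%, f = 40%.** u = 1 − 0.24/0.60 = 60%. Related risks of 33.3% and 50.0% average 40% (0.6 × 33.3 + 0.4 × 50.0) and have odds 0.5 and 1, so OR 2. Group sizes are 276.6 and 184.4.
- Any AE: 1 − 0.4 × 0.667 = 73.3% and 1 − 0.4 × 0.5 = 80.0%. OR = 4/2.75 = 1.45. SE = √(1/54.09 + 1/29.50) = 0.229, z = 1.64, power 37%.
- Related AE, s = 80%: risks 40% and 50%, OR 1.50. SE = 0.192, z = 2.11, power 56%.
- Related AE, s = 70%: risks 43.3% and 50%, OR 1.31. SE = 0.191, z = 1.41, power 29%.

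**Range.** Each cell shows OR, then power.

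| r | f | Any AE | Related, s = 80% | Related, s = 70% |
|---|---|---|---|---|
| 30% | 30% | 1.34, 22.2% | 1.46, 45.1% | 1.28, 22.6% |
| 30% | 50% | 1.31, 23.5% | 1.44, 47.6% | 1.27, 23.9% |
| 40% | 40% | 1.45, 37.4% | 1.50, 56.2% | 1.31, 29.0% |
| 50% | 30% | 1.61, 46.7% | 1.51, 52.0% | 1.31, 26.9% |
| 50% | 50% | 1.58, 54.1% | 1.51, 59.7% | 1.32, 31.3% |

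**Ambiguity.** Take the worked case and hold related risk at 40% in both groups. Let background risk be 55.6% and 66.7%, which averages 60%; the OR is 2.0/1.25 = 1.6. Any-AE risks are 1 − 0.6 × 0.444 = 73.3% and 1 − 0.6 × 0.333 = 80.0%. These are the same two percentages as before, now with no genotype effect on drug-caused events. The any-cause model cannot tell the two situations apart.

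**The SAP's own contrast.** The SAP has no ε4-carrier term. If 30-50% were carriers, Hardy-Weinberg proportions give an ε4/ε4 share of (1 − √(1 − c))² with c the carrier share: 0.163² = 2.7% to 0.293² = 8.6%, or about 12 to 40 of 461. With those group sizes in the same formulas, power for OR 2 is about 21-54% on perfectly classified related AEs and about 7-20% on any AE.

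**The case against.** The strongest reply is that the endpoint phrase is one undefined line in a synopsis and may simply mean AEs while on donepezil. The primary endpoint and the sample size both use AEs without regard to cause, and on that reading the model matches the endpoint. This reading is possible. It does not remove the point, because the SAP itself distinguishes AEs from AEs by relationship, and the plan should say which enters the APOE model.

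Other parts of the reply stand, and they limit what a reader might infer:
- *That a related-AE outcome would give power of 90-96%.* The formulas do give that for OR 2, but only with error-free causality judgement. The documents offer nothing to support that in an open-label trial without a comparator. The 80% and 70% columns are the fairer guide, and at 70% the related outcome is no better than any AE, or worse.
- *That the any-AE outcome is nearly saturated.* At 76% of 461, about 111 patients would have no AE, which is workable for logistic regression. Dilution comes from background events.
- *That related AEs should be the main outcome in all the risk-factor models.* Endpoint 4 covers APOE only. The models for age, weight, history and concomitant drugs are not tied to a drug-specific endpoint.
- *That the SAP claims a donepezil effect from these models.* It speaks only of correlations with AEs.

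Finally, relabelling events as related does not supply a comparator. Misjudged background events would leak into the related outcome too.

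**Conclusion.** The gap between the endpoint's wording and its only planned analysis is in the text. It is worth closing because the needed classification is already planned. Under the stated assumptions, a true OR of 2 on drug-caused AEs appears as about 1.3-1.6 on any AE, with power of 22-54%. Judged relatedness at 80% sensitivity and specificity gives an OR of about 1.4-1.5 and power of 45-60%. At 70% it gives about 1.3 and 23-31%, so most of the gain is lost.

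These sizes rest on a related-AE rate, a genotype share and an independence assumption that the documents do not supply. The binary group is not one of the SAP's contrasts; for ε4/ε4, power would be much lower on either outcome. The figures show a mechanism and do not forecast the trial's result. A reader might go further and conclude that the any-cause model is invalid or should be replaced. The documents do not support that: it remains a legitimate description of AEs during treatment. What fails is resting a statement about donepezil's own adverse events on that model alone.

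**What to change.** For endpoint 4, add to the SAP the same APOE logistic models with the outcome of at least one AE assessed as related to donepezil, reported beside the any-cause models. State which categories of the relationship assessment count as related. Add one sentence on interpretation: an APOE association seen only for any-cause AEs will be described as an association with AEs during treatment, and not as an effect of donepezil. The other risk-factor models can stay as planned.

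The cost is a short SAP change and one more set of models on a classification the SAP already tabulates, with no new visits, data or patients. The drawbacks are fewer events, one more set of results to interpret, and reliance on a subjective open-label judgement. For those reasons neither outcome should be read alone.

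### The adjusted adverse-event model can drop APOE, a named secondary endpoint, or exaggerate its odds ratio, because stepwise selection decides whether it is fitted

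*SAP*

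**What the plan says.** Protocol section 1.4 lists among the secondary endpoints "Correlation analysis between Apo-E genotyping and adverse events of donepezil". Protocol section 1.7 gives no method for it, so the method comes from the SAP alone.

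The SAP's safety paragraph works in two steps. Univariate logistic regressions come first, on a named list of candidates that includes APOE twice: as a six-level genotype and as ε4/ε4 present or absent. Then "Forward stepwise multivariate logistic regression analysis is subsequently performed to" assess the risk factors further, "using variables chosen from those used in the univariate analysis". The only tuning value given is SLSTAY=0.3, explained as "a significance value of 0.3 is required for a variable to stay in the multivariate model". In the closing paragraph a p value below 0.05 "is considered to indicate statistical significance", and this applies to all analyses.

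The SAP does not state an entry level, the rule by which variables are chosen from the univariate list, any term that is always fitted, or any multiplicity adjustment.

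**The concern.** Three features combine.

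- Nothing keeps APOE in the multivariable model. The adjusted result for a named secondary endpoint may simply not exist at the end of the study, and its absence would depend on the same data.
- A term that stays only if it looks large enough is, on average, overstated when it stays. A reader of the final model would see the survivors without that warning.
- The two APOE codings compete. The ε4/ε4 indicator is one level of the genotype variable, so the two cannot both be estimated in one model. Which one represents APOE would also be settled by the search.

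At stake is what the study can say about APOE after adjustment, and how much weight its other risk factors can bear.

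**Working it through.** **The plan's own figure.** Protocol section 1.1 gives 461 patients for a 95% CI of total width 8% at 76% incidence. The Clopper-Pearson interval has width 0.08005 at n = 460 and 0.07996 at n = 461, so 461 is reproduced. The enrolled number is 461 × 1.2 = 553.2, rounded up to 554. This calculation sizes the precision of the incidence. It does not size a risk-factor model.

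**Candidates (SAP).** 5 histories + 3 (age, gender, weight) + 2 APOE codings + 6 medication classes + 1 prior 5 mg duration = 17. In degrees of freedom: 5 + 3 + (5 + 1) + 6 + 1 = 21 nominal, of which 20 are estimable because of the nesting.

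**Information available.** The rarer outcome is having no adverse event: 0.24 × 461 ≈ 111, or 111/21 = 5.3 per nominal degree of freedom. With all 554: 0.24 × 554 ≈ 133, or 6.3.

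**Selection effect, by hand.** Assume one binary factor with 40% prevalence, 76% incidence in the unexposed, true OR 1.5 and n = 461.

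- Exposed incidence: odds (0.76/0.24) × 1.5 = 4.75, so 0.826.
- Variance of the log OR: 1/(184.4 × 0.826 × 0.174) + 1/(276.6 × 0.76 × 0.24) = 0.0377 + 0.0198 = 0.0576; SE = 0.240.
- To pass at 0.30, the estimated OR must exceed exp(1.036 × 0.240) = 1.28. To pass at 0.05, it must exceed exp(1.960 × 0.240) = 1.60, which is above the true value.

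The normal approximation then gives the drop rates and the mean OR among survivors. Three separate sets of stepwise simulations (17 candidates, n = 461, same true OR) are set beside it:

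| | Hand calculation | Simulations |
|---|---|---|
| Dropped, threshold 0.30 | 25% | 24–27% |
| Dropped, threshold 0.05 | 61% | 55–58% |
| Mean OR when kept, 0.30 | 1.69 | 1.68–1.70 |
| Mean OR when kept, 0.05 | 1.91 | 1.88–1.93 |
| Mean OR when always fitted | 1.54 | 1.53–1.60 |

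With entry at 0.30, the survivors that also reach p<0.05 average 1.91. For a true OR of 2.0, the simulated mean when kept is 2.09 (entry 0.30) or 2.18 (entry 0.05), against 2.08 in a full model.

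**APOE itself.** With assumed allele frequencies of 8%, 70% and 22% for ε2, ε3 and ε4, simulation drops both APOE codings in about 59–61% of trials (entry 0.30) or 92–93% (entry 0.05) when APOE has no effect. With an assumed true ε4/ε4 OR of 2, the figures are 43% and 84%. The ε4/ε4 group is small under these frequencies: 0.22² × 461 ≈ 22 patients.

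**False risk factors.** If no candidate has an effect and the 17 tests are independent, 1 − 0.95¹⁷ = 58.2%. Simulated under the global null at n = 461 and 76% incidence:

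- Stepwise: 57–63% with entry 0.30, and 52–54% with entry 0.05.
- Stepwise with entry and stay both at 0.05: 53%.
- One full model: 54–56%.
- Univariate screen alone: 54–57%.

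The largest gap between stepwise and the full model, 63% against 54%, arises only with very strong history–medication correlation (0.9).

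**The case against.** The case on the other side is substantial.

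- **The endpoint is not lost.** A reader might infer that APOE could go unreported. The documents do not support that: the univariate step tests both APOE codings without selection, and Protocol section 1.4 promises a correlation analysis, not an adjusted estimate. This stands. Only the adjusted result is at risk.
- **The 0.3 level is not the culprit.** A reader might blame it, or stepwise selection, for the roughly 60% chance of a false factor. The comparison above shows nearly the same rate in a full model and in the univariate screen. A lenient level also exaggerates less than a strict one (about 1.7 against 1.9). This stands.
- **Strong effects are safe.** At a true OR of 2.0 and entry 0.30, the exaggeration is negligible. This stands, though an effect that strong cannot be presumed.
- **The size rests on assumptions.** The entry level, choice rule, prevalences and effect sizes are not in the documents. This stands for the figures. The missing entry level is itself part of the problem, since the drop rate more than doubles across plausible values.
- **A full model with false-discovery-rate control is not clearly better.** For 17 independent tests at a true OR of 1.5 and prevalence of 20–50%, power falls from 32–46% to 7–14% under Benjamini-Hochberg. That is a real loss when screening for safety risk factors, so such a model is not required here.

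None of this answers the narrow point that the adjusted APOE result is left to selection.

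**Conclusion.** The point holds in limited form, as a minor improvement. The adjusted APOE result depends on a search whose entry level is unstated. A modest effect would be missing from the final model in roughly a quarter to 58% of trials, and overstated when present (about 1.7 to 1.9 for a true 1.5, against about 1.55 when always fitted). These figures assume a binary factor, n = 461, 76% incidence and entry between 0.05 and 0.30. They illustrate the mechanism and do not predict the APOE result.

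The chance of at least one false risk factor, about 58%, is a separate matter of multiplicity. It assumes that all 17 candidates are offered and none has an effect. The primary endpoint, adverse-event incidence, is untouched.

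**What to change.** Amend the SAP's safety paragraph as follows.

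1. Pre-specify one APOE coding for the multivariable model, either genotype or ε4/ε4 but not both. Choose it with the expected group sizes in mind.
2. Force that term into the model, and report its adjusted odds ratio with a 95% CI whatever its p value.
3. State the entry level and the rule for choosing variables from the univariate list.
4. Label the other selected factors exploratory, or print multiplicity-adjusted p values beside the raw ones, so that p<0.05 is not presented as an established risk factor.

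The Protocol's procedures place genotyping at Visit 2, so patients who leave earlier have no APOE value. The report should say how many the adjusted model omits.

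The cost is SAP wording, with no new data or patients. The downside is weaker claims for the non-APOE factors.
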